#### 1.4.2.2 PRELIMINARY DATA ON FUTURE TRIAL-RELATED OUTCOMES.

The primary outcome variable related to a future efficacy trial is alcohol use (as measured by the PROMIS Alcohol Use 7a and number of drinking days). The primary intermediate variables are self-efficacy and readiness to change drinking. We will describe pre-post changes in intermediate and outcome variables using descriptive statistics. T-tests will examine whether pre-post changes in TRAC differ significantly from pre-post changes in control. The goal of these analyses will be to estimate standard deviations for use in future studies. In exploratory analyses, we will include intermediate variables as covariates to model the relation between outcome variables and hypothesized mediators.

---

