- 5) meeting hazardous drinking criteria on the AUDIT-C questionnaire, defined as a score of 3 or higher for women/4 or higher for men (The AUDIT-C consists of items 1, 2, and 3 from the full AUDIT questionnaire);

Participants with severe psychopathology (psychosis, suicidal behavior, substance dependence) will be excluded from the study. The AUDIT questionnaire will be administered as part of screening to determine alcohol dependence; if survivors have a score of 20 or higher, they will be referred to UKMCC Social Work.

**RCT:** n=50, Intervention group (TRAC) n=25, and Control group (education and monitoring) n= 25. To be eligible to participate in the RCT, survivors must meet the following criteria:

- 1) diagnosed with cancer between age 15-39;
- 2) currently age 18-39;
- 3) 3 months - 15 years posttreatment (hormonal therapy allowed);
- 4) report unhealthy alcohol use in the previous 3 months, defined as:
  - a. exceeding moderate daily drinking levels (more than 1 drink/day for women, more than 2 drinks/day for men) at least 3 times in the past 3 months OR
  - b. engaging in heavy weekly drinking (more than 7 drinks/week for women, more than 14 drinks/week for men) at least once in the past 3 months OR
  - c. engaging in binge drinking (more than 3 drinks/sitting for women, more than 4 drinks/sitting for men) at least once in the past 3 months; OR
- 5) meeting hazardous drinking criteria on the AUDIT-C questionnaire, defined as a score of 3 or higher for women/4 or higher for men (The AUDIT-C consists of items 1, 2, and 3 from the full AUDIT questionnaire)
- 5) Reside in the United States

Just as with the Open Pilot, participants with severe psychopathology will be excluded from the study. The AUDIT questionnaire will be administered as part of screening to determine alcohol dependence; if survivors have a score of 20 or higher, they will be referred to UKMCC Social Work (if a patient at UK HealthCare). Non-UK patients will be provided with information for SAMHSA's treatment finder, national helpline, and local resources based on the zip code provided at the time of screening. Survivors who score a 20 or higher on the AUDIT questionnaire will not be eligible for the study, as this study is not designed to manage alcohol dependence and its immediate health risks.

Enrollment will begin February 2022 and continue through May 2023 or until the proposed participant pool is reached.

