#### Study Procedures: Randomized Controlled Trial

To achieve Aim 2, we will conduct a pilot RCT of the TRAC-AYA intervention with a total of 50 participants (25 per condition).

Participants in the RCT will be enrolled in the study for a total of 10 weeks, whether they are in the intervention or control group. If participants are unable to complete monitoring or intervention tasks within the initial 4-week period, they will be given up to 6 weeks to complete the tasks before being considered noncompleters. The delayed post-test is delivered 4 weeks after completion of all monitoring/intervention tasks at 10 weeks.

Intervention (Group A) participants will complete 4 intervention sessions on a weekly basis, conducted via phone or videoconference (HIPAA-compliant Zoom), according to participant preference. These sessions will be audio recorded. Participants will also complete daily self-monitoring of alcohol use using mobile surveys and breathalyzers for 6 weeks. Control (Group B) participants will receive educational materials regarding alcohol use and will complete mobile monitoring of alcohol use in the same manner as Group A for 6 weeks. All RCT participants will complete a baseline assessment survey upon enrollment, a follow-up survey once all intervention/monitoring tasks are completed at 6 weeks, and a qualitative exit interview which will be audio recorded. All RCT participants will also complete a delayed post-test assessment at 10 weeks, 4 weeks after they complete the follow-up survey.

The total estimated maximum time commitment for RCT Group A (Intervention) participants is 13 hours, 45 minutes. The total estimated maximum time commitment for RCT Group B (Control) participants is 10 hours, 45 minutes.

All RCT participants will receive up to \$315 in Amazon e-gift cards for their participation.

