**RCT Enrollment:** The RCT will enroll 50 participants, 25 per condition. First, we will administer a screener to verify participants meet all inclusion criteria. If patients do not wish to be screened and are not interested in participating in the study, we will ask that they complete a brief Refusal to Screen Questionnaire to indicate why and collect basic demographic information to inform generalizability of the obtained sample. If participants complete the screener and indicate that they are interested in learning more about the study, we will collect their contact information and a member of the study team will follow-up with the participant to obtain informed consent and complete enrollment if they meet all eligibility criteria. Pre-screened participants who screen eligible and indicate interest in the study will be automatically directed to the approved eConsent in REDCap. If participants are determined to be eligible for the study and

consent to enroll, we will also collect information for at least 1 emergency contact (participants have the option to provide a backup emergency contact). We will contact these individuals only in cases of extreme distress, adverse events, or threats of self-harm. We will make clear to participants that we will not specify the nature of the research study to these individuals. If the participant is a patient at UK HealthCare, researchers will also contact their medical care team should any of these cases arise. Once participants have been enrolled in the study they will complete a baseline questionnaire, which may be done in-person, online via REDCap, via phone, or via mail per participant preference. It will ask about 1) Alcohol use, consequences, and attitudes, 2) Tobacco and other substance use, 3) Cancer history, 4) Overall physical/mental health, 5) Healthcare usage and history, 6) Financial toxicity, 7) Health literacy, 8) Coping Self-efficacy, 9) Social support, and 10) Drinking refusal self-efficacy.

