**RCT Data Collection:** For Group A (Intervention) participants only, a brief treatment expectations questionnaire assessing their attitudes toward the intervention will be administered. Additionally, after each counseling session, Group A participants will complete a short intervention session rating questionnaire. All counseling sessions will be audio recorded in order to provide supervision and fidelity checks for the interventionist. Both Group A and Group B (Control) will complete surveys assessing daily alcohol intake each morning and report blood alcohol content (via breathalyzer readings uploaded to REDCap) each evening until they have completed 42 total days of monitoring. In the unlikely event that participants are not able to upload their breathalyzer reading to REDCap, they will text a screenshot of their reading to the study coordinator on a study cell phone who will upload the reading to REDCap on the participant's behalf. Readings will be deleted from the study cell phone immediately after they are uploaded into REDCap. After all intervention/monitoring tasks are completed at 6 weeks, both groups will complete a follow-up questionnaire, which may be done in-person, online via REDCap, via phone, or via mail per participant preference. The follow-up questionnaire matches the initial baseline questionnaire, with additional questions about satisfaction with the intervention being shown to Group A (Intervention). All RCT participants will also complete a 20-30 minute semi-structured exit interview after completing the follow-up questionnaire. This interview will ask about perceptions of monitoring technology, perceived effects of monitoring, need for additional support, and suggestions for improvement. In addition to these, Group A (Intervention) participants will be asked questions regarding overall satisfaction with the TRAC program, reactions to session content, length, and components. The study coordinator will conduct the interviews. Interviews will be audio recorded and transcribed using a transcription service. Finally, 4 weeks after participants complete the follow-up survey, RCT participants will complete the delayed post-test survey at 10 weeks. This final data collection instrument matches the follow-up survey, but will not contain questions relating to satisfaction with the TRAC program. Participants may complete the delayed post-test in-person, online via REDCap, via phone, or via mail per participant preference.

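### The arm comparison on alcohol outcomes rests on t-tests of pre-post change alone; adjusting for the outcome's own baseline would be a cheap gain in precision

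*Combined protocol and SAP*

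**What the plan says.** SAP section 1.4.2.2 names PROMIS Alcohol Use 7a and number of drinking days as the outcomes for a future efficacy trial. It first promises description: "We will describe pre-post changes in intermediate and outcome variables using descriptive statistics". It then gives the only specified comparison between arms: "T-tests will examine whether pre-post changes in TRAC differ significantly from pre-post changes in control". The stated purpose is: "The goal of these analyses will be to estimate standard deviations for use in future studies".

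Three other places come near baseline adjustment or an arm comparison, but none supplies an adjusted one:

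- The exploratory model in section 1.4.2.2 has covariates, but they are the intermediate variables (self-efficacy and readiness to change), used to study mediation.
- SAP section 1.4.2.1 uses baseline scores only to describe participants who drop out or do not adhere.
- The protocol's Study Design section says that daily monitoring data will allow the groups to be compared, but gives no method.

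On data, the protocol's Data Collection & Research Materials section says of the RCT baseline questionnaire: "It will ask about 1) Alcohol use, consequences, and attitudes". It adds: "The follow-up questionnaire matches the initial baseline questionnaire". Daily diaries are described only after enrollment: "Both Group A and Group B (Control) will complete surveys assessing daily alcohol intake each morning".

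**The concern.** A change score subtracts the whole baseline value, which amounts to fixing the regression slope of follow-up on baseline at 1. When the true slope differs, part of the baseline noise stays in the comparison. ANCOVA estimates the slope and removes that part. Any pre-post change already needs the baseline value, so the adjustment uses information the planned analysis must have.

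The analysed arms may be small. At the hypothesized 60% retention, equal across arms, there would be 12 completers per arm from the SAP's 40 participants (0.60 × 20) or 15 from the protocol's 50 (0.60 × 25). In arms of this size chance baseline differences are not negligible: with 25 per arm, the standard error of the baseline difference is √(2/25) = 0.28 SD.

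At stake is the precision of a secondary, preliminary estimate, and how directly its output can be used to plan a trial analysed by ANCOVA. The primary endpoint and the feasibility criteria do not depend on it.

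**Working it through.** **No figure to reproduce.** The documents state no SD, correlation, effect size or power for this comparison. The power statement in SAP section 1.2 concerns adherence only. All values of rho (the baseline-follow-up correlation) and of the variances below are therefore assumptions, and the results apply to a linear analysis.

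**Inputs from the documents.** Allocation is 1:1 with 25 per arm in the protocol (Study Procedures: Randomized Controlled Trial). The SAP has 40 in total, so 20 per arm if 1:1. Hypothesized retention is 60% (SAP section 1.4.2.1).

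**Identity.** Let s0 and s1 be the baseline and follow-up SDs.

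- Var(change) = s0² + s1² − 2·rho·s0·s1
- Var(ANCOVA residual) = s1²·(1 − rho²)
- Difference = (s0 − rho·s1)², which is never negative

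**Small-sample cost of estimating the slope.** The ANCOVA variance is inflated by (N − 3)/(N − 4), where N is the total analysed: 47/46 = 1.0217 at 25 per arm and 21/20 = 1.0500 at 12 per arm. If the true slope were exactly 1, ANCOVA would gain nothing and pay this factor. The ratio of change-score to ANCOVA variance would then be 1/1.0217 = 0.98 or 1/1.0500 = 0.95.

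**Case 1: equal variances.** The large-sample ratio is 2/(1 + rho), then divided by the factor.

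| rho | Large sample | 25 per arm | 12 per arm |
|---|---|---|---|
| 0.3 | 1.538 | 1.51 | 1.47 |
| 0.5 | 1.333 | 1.31 | 1.27 |
| 0.7 | 1.176 | 1.15 | 1.12 |
| 0.9 | 1.053 | 1.03 | 1.00 |

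**Case 2: restricted baseline.** RCT entry requires unhealthy drinking and has an upper limit: "Survivors who score a 20 or higher on the AUDIT questionnaire will not be eligible for the study". As an illustration, suppose entry keeps only the upper half of a standard normal baseline. Its variance falls to 0.363 (SD 0.603). With follow-up = rho·baseline + error and error variance 1 − rho², the ratio is 1 + (1 − rho)²·0.363/(1 − rho²). Here rho is the correlation before restriction. Within the restricted sample the same rows correspond to about 0.19, 0.33, 0.51 and 0.78, so they should not be read row for row against case 1.

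| rho (unrestricted) | Large sample | 25 per arm | 12 per arm |
|---|---|---|---|
| 0.3 | 1.196 | 1.17 | 1.14 |
| 0.5 | 1.121 | 1.10 | 1.07 |
| 0.7 | 1.064 | 1.04 | 1.01 |
| 0.9 | 1.019 | 1.00 | 0.97 |

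A simulation of 40,000 trials per cell agreed with both tables to within 0.01 and showed a mean error of about zero for both estimators.

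**SDs for planning.** Under equal variances, residual SD/change SD = √((1 + rho)/2) = 0.806, 0.866, 0.922 and 0.975 at rho 0.3, 0.5, 0.7 and 0.9. If s0, s1 and the change SD sd are all reported on the same completers, then rho = (s0² + s1² − sd²)/(2·s0·s1) and residual SD = s1·√(1 − rho²). For example, s0 = s1 = sd = 1 gives rho = 0.5 and residual SD 0.866. From the change SD alone the residual SD cannot be recovered. For scale, the chi-square 95% CI for an SD runs from 0.83 to 1.25 times the estimate at 48 df, and from 0.77 to 1.42 at 22 df.

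**The case against.** The strongest reply is that this is a preference between valid methods. The change-score contrast is unbiased under randomisation, no decision rule uses its p-value, and the section's declared aim is to estimate SDs, not to show efficacy. Every rho is assumed, and in the restricted-baseline case at 0.7 to 0.9 the ratio is 0.97 to 1.04, practically nothing. The protocol's Informed Consent Process section says that the study is closed to enrollment, so prespecification may no longer be possible. All of this stands and keeps the point minor. It does not remove the asymmetry between a small, bounded cost and a gain that may be material.

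A reader might infer more than the documents support:

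- **That the t-test gives a wrong answer.** It does not; only precision is affected.
- **That ANCOVA is strictly free.** It is cheap, but can lose about 2% at 25 per arm and 5% at 12.
- **That the gain could be larger still.** With a baseline SD 1.3 times the follow-up SD and rho 0.5, the ratio would be 1.81 at 25 per arm. Nothing in the documents supports a wider baseline, and the entry limits suggest a narrower one.
- **That the SAP fails to deliver planning SDs.** Section 1.4.2.2 commits to descriptive statistics and to estimating SDs. It does not say which SDs, and it does not mention the correlation, but that is missing detail. Harm would follow only if the change SD alone were reported, and planning an ANCOVA trial on it would then be conservative. A detailed protocol is listed as an attachment but not supplied, so the silence can be checked only in the text at hand.
- **That the choice of planning SD is always lost in sampling error.** At rho 0.3 with equal variances the residual SD is 0.806 of the change SD, outside the 48-df lower limit of 0.834. In the other cells shown it lies within the limits.

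**Conclusion.** The point holds as a low-priority improvement. The only specified arm comparison leaves out the outcome's own baseline, and ANCOVA would be at least as precise in large samples under 1:1 allocation. At 25 per arm the variance penalty for the t-test ranges from 51% down to 3% under equal variances, and from 17% to none if entry halves the baseline range. These sizes rest on assumed correlations and variances, on a linear model, and on the protocol's 25 per arm; the SAP's 40 participants would shift them only slightly. The choice of SDs to report is a reporting refinement, secondary to the baseline adjustment.

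**What to change.** In SAP section 1.4.2.2, make the arm difference an ANCOVA estimate: follow-up value on arm and the baseline value of the same measure, with a 95% CI. Use the 6-week follow-up (T1), which the section does not currently specify, and analyse the 10-week survey in the same way. Keep the change-score description and t-test as supportive.

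For drinking days, adjust only for a baseline from the same source and the same time window, if one was collected. Diary data begin after enrollment, so a diary follow-up should not be paired with a questionnaire baseline.

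If outcome data have already been examined, label the ANCOVA post hoc.

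As a minor addition, tabulate on the same completers, with CIs and n per arm, the baseline, follow-up and change SDs, the baseline-follow-up correlation and the ANCOVA residual SD.

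The cost is a few lines of text and one degree of freedom. The PROMIS measure needs no data beyond what its change score already requires. For drinking days this depends on whether a matching baseline exists, which the supplied documents do not show. The table can be added at any time.

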## Objectives

List your research objectives. Please include a summary of intended research objectives in the box below.

Posttreatment rural AYAs are an underserved group at risk for increased alcohol use and poor access to interventions, ultimately leading to poorer physical and mental health. mHealth interventions are recommended for AYAs and have shown high acceptability and positive health effects. To address the lack of mHealth interventions for alcohol use among rural AYAs, we will adapt and pilot an existing mHealth intervention (TRAC) to reduce alcohol use. We will conduct the study in Kentucky, which leads the nation in cancer incidence and mortality, has a higher incidence of AYA cancers compared to other states, is 40% rural, and encompasses over 100 medically underserved areas. The study team has expertise in mHealth interventions, cancer survivorship, clinical trials, and AYA oncology. Thus, we are well-equipped to complete the following Aims:

1. Adapt and refine TRAC for rural posttreatment AYAs. We will conduct semi-structured interviews with key informants (N=14; 6 AYAs, 8 AYA oncology clinicians and community advocates), and conduct an open pilot study (i.e., fully implement the intervention) with a small number of patients (N=4; 2 TRAC, 2 control comparison) to adapt the content and delivery procedures of TRAC for rural AYA cancer survivors, resulting in TRAC-AYA.

2. Test the feasibility and acceptability of conducting an RCT of TRAC-AYA with AYAs (N=50; 25 TRAC, 25 control comparison). Comparison group will receive alcohol monitoring and educational materials. The primary feasibility outcome will be enrollment (=60% of eligible AYAs approached enroll). Secondary feasibility outcomes include retention (=60% complete follow-up) and intervention adherence (=70% complete =60% of intervention sessions; alcohol monitoring =70%). Acceptability will be assessed with mean ratings (scores =7 out of 10) of intervention relevance, helpfulness, and convenience. We will also obtain preliminary data on alcohol use frequency, quantity, binge drinking, and health (PROMIS-29).

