### 1.2 SAMPLE SIZE DETERMINATION

The sample size of 40 is based on the goal of estimating the probabilities and means for 3 feasibility outcome measures (enrollment  $\geq$  60% [primary], retention  $\geq$  60%, adherence [defined as  $\geq$ 70% completing at least 60% of sessions]). Assuming a negative binomial distribution and true probability of enrollment of 60%, the probability that we would have to approach 55 or more people to recruit 40 is  $<0.05$ . If we approach  $\geq$ 55 AYAs to enroll 40, it is unlikely the true probability of enrollment is 60% or greater, concluding a future efficacy study may not be feasible. Out of 40 AYAs, if the true probability of retention is 60% we expect at least 19 AYAs will be retained (i.e., probability of  $n \leq 19$  retained given true retention probability of 60% is  $<0.05$ ), so if more than 21 AYAs are not retained, an efficacy study may not be feasible. We have 80% power (using a 2-tailed alpha of 0.05) to detect an adherence proportion of 0.72 if we assume a null hypothesis adherence proportion of 0.50.

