#### 1.4.2 AIM 2 ANALYSES

##### 1.4.2.1 FEASIBILITY

Enrollment: the number of AYAs enrolled divided by the number of eligible AYAs approached (hypothesized value = 60%).

Retention the percentage of AYAs who complete baseline and follow-up questionnaires (T0, T1; hypothesized value = 60%).

Adherence: the percentage of AYAs who complete at least 75% of sessions in 8 weeks (hypothesized value = 70%); alcohol monitoring hypothesized value = 70%).

We will calculate 95% CIs for feasibility measures to determine the range of estimates that are consistent with our data. We will use one-sample negative binomial probabilities and tests of binomial proportions to compare to hypothesized values. We will summarize reasons for ineligibility and refusal and compare AYAs who drop out or do not adhere by demographic and clinical characteristics, and baseline scores of the measures (e.g., PROMIS-29, alcohol use). We will investigate differences in AYA enrollment, retention, or adherence by sociodemographic and clinical characteristics (e.g., cancer type) to identify populations for a future study.

---

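### SAP 1.4.2.2 compares arms with an unadjusted t-test on change among completers; adjusting for the baseline value is more precise and protects against dropout that depends on baseline drinking differently in the two arms

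*Combined protocol and SAP*

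**What the plan says.** SAP 1.4.2.2 names alcohol use (PROMIS Alcohol Use 7a and number of drinking days) as the outcome for a future efficacy trial. It plans descriptive statistics of change, and then: "T-tests will examine whether pre-post changes in TRAC differ significantly from pre-post changes in control". It gives the purpose as follows: "The goal of these analyses will be to estimate standard deviations for use in future studies".

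SAP 1.4.2.1 defines retention as "the percentage of AYAs who complete baseline and follow-up questionnaires (T0, T1; hypothesized value = 60" per cent. The protocol's Objectives use the same figure as a criterion: "Secondary feasibility outcomes include retention (=60% complete follow-up". SAP 1.2 prints it as at least 60%.

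The sample differs between the two parts. The protocol (Study Procedures: Randomized Controlled Trial) says "we will conduct a pilot RCT of the TRAC-AYA intervention with a total of 50 participants (25 per condition", while SAP 1.2 says "The sample size of 40 is based on the goal of estimating the probabilities and means for 3 feasibility outcome measures".

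The protocol's RCT Data Collection text says that the follow-up questionnaire matches the baseline one, so T0 values should be available for adjustment. It also says that "RCT participants will complete the delayed post-test survey at 10 weeks", four weeks after the follow-up survey. The Aim 2 analyses in the SAP do not mention that later survey. The SAP states no missing-data method for the change comparison. It plans only to compare participants who drop out or do not adhere on demographic, clinical and baseline measures.

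**The concern.** A t-test on T1 minus T0 uses only people who have both values and makes no use of baseline except by subtracting it. Two costs follow.

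The first is precision. Unless the correlation between T0 and T1 is close to 1, subtracting the whole baseline value adds noise that a regression adjustment would not.

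The second is selection. Participants enter because of recent unhealthy or hazardous drinking, so regression to the mean is to be expected, and change is then correlated with baseline. If the completers in the two arms differ in baseline drinking because different people left, the change contrast moves even when the intervention does nothing.

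The arm difference and its SD are meant to inform a definitive trial. The t-test's SD is the change-score SD, which is not the one needed if that trial adjusts for baseline.

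**Working it through.** **The plan's own figures.** No sample size or power is stated for the t-test. The only stated calculation that uses 60% retention is in SAP 1.2: the probability that 19 or fewer of 40 are retained is put below 0.05. The exact binomial value is 0.074 (18 or fewer gives 0.039). That discrepancy is separate and does not affect this point.

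**Participants without a change score.** N × (1 − retention):
- Protocol: 50 × 0.40 = 20, leaving 30 (binomial 95% range 23 to 37).
- SAP: 40 × 0.40 = 16, leaving 24.
- At 80% retention of 50: 50 × 0.20 = 10.

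**Precision.** Assume a roughly normal outcome with SD 1 at both times, correlation r, and 15 completers per arm (50 × 0.60 / 2).
- Change score: variance 2(1 − r). At r = 0.6 this is 0.80, SD 0.894, and SE = 0.894 × √(2/15) = 0.33.
- Baseline-adjusted: residual variance 1 − r² = 0.64, SD 0.80. SE = 0.80 × √(2/15) × √(1 + 1/26) = 0.30, the last factor allowing for the estimated slope.
- Simulation with random dropout gives the same 0.33 and 0.30.

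**Bias under no effect.** Change equals −(1 − r) × baseline plus noise. The bias is therefore −(1 − r) × (mean baseline of TRAC completers − mean baseline of control completers). Assume 60% retained in each arm, random dropout in control, and heavier drinkers likelier to leave TRAC at a log-odds slope of 0.75 or 1.5 per SD. TRAC completers then sit about 0.27 or 0.43 SD lower at baseline.

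| Dropout pattern | r = 0.3 | r = 0.6 | r = 0.8 |
|---|---|---|---|
| TRAC only, slope 0.75 | 0.7 × 0.27 = 0.19 | 0.4 × 0.27 = 0.11 | 0.2 × 0.27 = 0.05 |
| TRAC only, slope 1.5 | 0.7 × 0.43 = 0.30 | 0.4 × 0.43 = 0.17 | 0.2 × 0.43 = 0.09 |
| Same slope and retention in both arms | 0.00 | 0.00 | 0.00 |

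Simulation agrees to within about 0.01 SD, and the baseline-adjusted estimate on the same completers is biased by about 0.00 throughout.

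**Other patterns, slope 1 per SD.**
- Same slope but retention of 50% against 70%: bias 0.11, 0.08 and 0.05 SD at r = 0.3, 0.5 and 0.7.
- Slopes of opposite sign in the two arms, an extreme case: 0.46, 0.33 and 0.20 SD.
- Effect varying with baseline and equal dropout: a true difference of −0.30 SD became −0.23 with the t-test and also −0.23 with baseline adjustment without an interaction.

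**Consequence for the SDs.**
- Selective dropout lowers the completers' change SD by about 1 to 3%.
- Sampling error is larger. The 95% interval for a pooled SD runs from 0.83 to 1.25 times the estimate with 25 per arm, and from 0.79 to 1.35 times with 15 per arm.
- Change-score variance over residual variance is 2(1 − r)/(1 − r²) = 2/(1 + r), which is 1.25 at r = 0.6 and 1.54 at r = 0.3. A baseline-adjusted trial sized from the change SD would be too large by that factor.

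**The case against.** The strongest reply is that this is a pilot whose stated aim here is to estimate SDs, and those barely move under selective dropout. That stands for selection bias in the SD. It does not cover the arm contrast, which the SAP also tests, or the choice of SD to carry forward.

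A second reply is that nothing in the documents shows dropout differing by arm: monitoring and payment are the same in both. This also stands as far as it goes. The total time commitment does differ (up to 13 h 45 min for TRAC and 10 h 45 min for control), so a difference is plausible, but the documents do not predict one. Even then, at r = 0.6 a bias of 0.11 to 0.17 SD is about one third to one half of the standard error (0.11/0.33 and 0.17/0.33).

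A reader might infer that the plan expects to lose 40% of participants. It does not say so. The 60% is a feasibility threshold and a hypothesized value, so 20 (or 16) is the loss if the threshold is only just met.

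A reader might also expect the 10-week survey to recover those who miss T1. It is timed from completion of T1, so it may recover few of them. The benefit shown above comes from the baseline covariate, not from including every randomised participant.

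**Conclusion.** The point holds as a recommendation to use a better method for a secondary analysis. The unadjusted change comparison is less precise than a baseline-adjusted one (SE about 0.33 against 0.30 SD at r = 0.6). It can also be biased, by about 0.05 to 0.30 SD over r = 0.8 to 0.3, when dropout depends on baseline drinking in one arm and not in the other.

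The tempting stronger reading is that baseline-related dropout in itself biases the contrast, or that the pilot estimates are likely to mislead. The documents do not support either. Equal dependence with equal retention gives no bias if the effect is constant, and the documents are silent on how dropout will differ by arm.

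The correlations, dropout slopes and normal outcome are assumptions. Number of drinking days in particular may be skewed or bounded. The primary feasibility endpoint, enrollment, is unaffected.

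**What to change.** In SAP 1.4.2.2, replace the t-tests with a comparison of T1 by assigned arm, adjusted for the T0 value of the same outcome. ANCOVA is enough. An equivalent repeated-measures model with baseline constrained equal across arms could also use the 10-week survey where it is available. Report the arm difference, the residual SD and the change-score SD, each with a 95% confidence interval. Keep the t-test as a sensitivity analysis labelled as completers only. State how a missing T1 is handled, show the planned dropout comparison on baseline scores separately by arm, and reconcile the sample size of 40 with 50.

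The cost is SAP wording and slightly more analysis, with no new data. The adjusted analysis rests on a missing-at-random assumption. Without an arm-by-baseline interaction, it does not remove bias if the effect varies with baseline; with about 12 to 15 completers per arm, such an interaction would be poorly estimated, so this limit should be stated in the SAP.
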